6.2.2 Infusion Rates

For pump-assisted infusions, the volume and flow rate will be determined according to the pump display readings. As it is physically not possible to perform manual push at a constant rate, and it is performed in clinical practice by series of short manual pushes on the syringe plunger with small breaks between them, average flow rate per infusion in this cohort will be estimated by dividing volume infused in milliliters by the time of infusion in minutes.

The subject electronic diary (eDiary) for study participants in the Manual Push Cohort will provide recommendations of infusion duration depending on the actual dose (volume) to be infused and the target flow rate in mL/min for every subject using the following calculations (Table 2). If the eDiary is not available, a back-up paper diary will be provided for patient use until the eDiary becomes available. As soon as the eDiary is available, the data in the back-up paper diary will be entered into the eDiary. The back-up paper diary, if used, will be retained as a source document. During the time period when a back-up paper diary is in use, designated site staff will contact the subject on a weekly basis to ensure recording of infusion data and any AEs.

Table 2. Infusion Time

Volume, mL \ Flow rate, mL/min	0.5	1	2
	Infusion Time, minutes		
2	4	2	1
3	6	3	1.5
4	8	4	2
5	10	5	2.5
6	12	6	3
7	14	7	3.5
8	16	8	4
9	18	9	4.5

Flow rate, mL/min Volume, mL	0.5	1	2
10	20	10	5
11	22	11	5.5
12	24	12	6
13	26	13	6.5
14	28	14	7
15	30	15	7.5
16	32	16	8
17	34	17	8.5
18	36	18	9
19	38	19	9.5
20	40	20	10

6.3 Treatment Compliance

All doses of IgPro20 will be administered by SC infusion, with an office visit every 4 weeks, where the dose will be administered by the subject under the observation of the study staff; the remainder of the infusions will be done at home after confirmed and observed training at the first infusion (office visit). Treatment compliance will be monitored by reviewing the subject eDiaries and counting the used vials, the results of which should be documented.

7. Contraindications, Permitted Therapies and PROHIBITED Therapies

7.1 Contraindications and Precautions to Further Dosing

IgPro20 is contraindicated in subjects:

- Who have had an anaphylactic or severe systemic reaction to the administration of human immune globulin or to components of the immunoglobulin formulation, such as polysorbate 80 in IgPro20.
- With hypersensitivity to homologous immunoglobulins, especially in the rare cases of immunoglobulin A (IgA) deficiency when the subject has antibodies against IgA.
- With hyperprolinemia type I or II.

Full details of guidance on precautions for IgPro20 can be found in the Investigator's Brochure and Prescribing Information.

7.2 Permitted Therapies

The following therapies are PERMITTED during the study:

- Any medications that do not have the primary purpose of masking local or systemic AEs, and that are taken by the subject on a regular basis.
- Prescribed medications required for the management of chronic medical conditions
- Over the counter medications and dietary supplements.

7.3 Prohibited Therapies

The following therapies are NOT PERMITTED during the study:

- Any immunoglobulins other than IgPro20 provided for the study.
- Any other investigational product at any time during the study.
- Any medications with the primary purpose of masking local or systemic AEs (including but not limited to analgesics and anesthetics +/-12h around the infusion).
- Any systemic immunosuppressants that can affect serum IgG concentration (except for stable steroid doses required for pre-existing conditions).

Subjects are not to be enrolled into the study if they receive any prohibited therapy or any therapy in a prohibited dosage that cannot be discontinued or reduced to a permitted dose before enrollment.

If administration of any prohibited therapy becomes necessary during the study for medical reasons, the subject may be withdrawn from further study participation.

7.4 Dietary and Lifestyle Restrictions

Not applicable.

7.5 Overdose

Overdose is defined as the accidental or intentional infusion or ingestion of any dose of a product that is considered excessive. The effects of any potential overdose with IgPro20 have not been studied.

8. Study Procedures and Visit Schedule

8.1 Clinical Procedures

The clinical procedures related to demographics and safety are provided in Table 3. All other clinical procedures are provided in Table 4. Refer to the Laboratory Manual for detailed instructions on how the assessments should be performed.

Table 3. Clinical Procedures: Demographics and Safety Evaluation

Assessment	Description
Demographics	Date of birth, age, sex, and race.
Medical history	Relevant medical history. PID history, including specific PID diagnosis, date of diagnosis, and historic pre-treatment serum IgG level at the time of PID diagnosis. Contraception method. Current/concomitant therapies.
Pregnancy test	Blood test for beta-human chorionic gonadotropin.
Physical examination	As per the site's standard procedure
Vital signs	
 Blood pressure (systolic and diastolic) and respiratory rate after the subject has rested in a sitting or supine position ≥ 5 minutes Pulse rate (per minute) will be measured from the radial pulse counted manually or with an automatic blood pressure monitor over ≥ 15 seconds Body temperature using sublingual or tympanic measurement (consistent method to be throughout the study for a given subject) Body weight Height.
Hematology	
 Erythrocytes Leukocytes Differential count^a Hematocrit Mean corpuscular volume Hemoglobin Platelets
Biochemistry	
 Alanine aminotransferase Bicarbonate Gamma glutamyl transferase Urea or BUN Alkaline phosphatase Chloride Potassium Aspartate transaminase Creatinine Sodium

BUN = blood urea nitrogen; IgG = immunoglobulin G; PID = primary immunodeficiency.

^aDifferential count: neutrophils, eosinophils, lymphocytes, monocytes, basophils.

Table 4. Clinical Procedures

Procedure	Description
Serum IgG assessment	
 Blood samples will be collected for assessment of serum IgG trough levels.

IgG = immunoglobulin G.

The timing and frequency of all clinical procedures are described in the [Schedule of Assessments](#). Refer to the Laboratory Manual for details about the collection, storage, handling and transportation of biological specimens.

8.2 Retention of Samples

Samples will not be retained after the completion of the study.

8.3 Concomitant Therapies

All drugs and/or procedures currently being administered to a subject at the time of signing informed consent, and which continue to be taken in addition to IgPro20 during the study, are regarded as concomitant therapies and must be documented as such in the eCRF.

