- b. Biochemistry: sodium, potassium, chloride, bicarbonate, urea, creatinine, gamma glutamyl transferase, alkaline phosphatase, alanine aminotransferase, aspartate transaminase.
- c. eDiary will be used for collecting infusion parameters and adverse events. A paper diary is available as a back-up if the eDiary is unavailable. As soon as the eDiary becomes available, the data from the paper diary must be transcribed into the eDiary and the paper diary retained as source.

Study Number: IgPro20_4004
Study Product: IgPro20

- d. Within approximately 1 hour before next infusion.
- e. Subjects who drop out of the study due to reasons other than 'consent withdrawn' or 'lost to follow-up' will be followed up by weekly telephone calls by site personnel for the full duration of their planned study participation, in order to collect information on AEs.
- f. Office visit at Weeks 1, 5, 9, 13, and End of Study.
- g. eDiary / back-up paper diary collection and review. The eDiary device will also be collected, if provisioned.

Study Number:

IgPro20_4004

Study Product:

IgPro20

Schedule of Assessments – Manual Push Flow Rate & Pump-Assisted Volume Cohorts

Study Period	Screening	Forced Upward Titration												End of Study
Study Day	-35 to -7	1	8	15	22	29	36	43	50	57	64	71	78	85±1 day
Week number		1 ^f	2	3	4	5 ^f	6	7	8	9 ^f	10	11	12	13 ^f
Informed consent/assent	X													
Inclusion / exclusion criteria	X	X												
Medical history and demographics	X													
Pregnancy test	X													X
Physical examination	X													X
Systolic and diastolic blood pressure, respiratory rate, pulse rate, and body temperature	X	X				X				X				X
Body weight and height	X													X
Hematology ^a & biochemistry ^b	X													X
Infusion training / supervised infusion / supervised entry of infusion data in the subject eDiary		X				X				X				
IgPro20 dispensation and IRT update		X				X				X				
Subject eDiary ^c training and review		X				X				X				X ^g
IgPro20 administration (weekly for pump-assisted infusion; 2 to 7 times per week for manual push)		X	X	X	X	X	X	X	X	X	X	X	X	
Serum IgG trough level ^d		X												X
Adverse events (including injection site assessments) ^e	X	X	X	X	X	X	X	X	X	X	X	X	X	X
Concomitant therapies	X	X				X				X				X

eDiary = electronic diary; IgG = immunoglobulin G; IgPro20 = Hizentra; IRT = Interactive Response Technology.

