8.4.2.2 Weeks 2 (Day 8±1), 3 (Day 15±1) & 4 (Day 22±1)

The following procedures will be conducted and documented **at home**:

- Administer IgPro20. Infusion data should be recorded in the subject eDiary / back-up paper diary.
- Evaluate for AEs (including injection site reaction[s]) and record any findings in the subject eDiary / back-up paper diary.

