Any deviation from the above defined criteria for each infusion parameter step will be considered a ‘failure’ (i.e. invalid infusion) in the analysis of this set of infusion parameters. However, if it is conducted as stated in the protocol but at a lower parameter level, it can be evaluated for the actual parameter as conducted. For example, if a subject was scheduled to a test volume of 50 mL/injection site, but for some reasons tested 45 mL/injection site, it will not count for the 50 mL level, but if that infusion was otherwise uneventful and performed in full without interruption, it will be considered valid for the 45 mL/injection site level, even though it was not planned. These unplanned parameter levels will be summarized in a separate column “Other” in the tables depending on the scenario. The data may not be summarized if the unplanned level only occurs in one subject. If all subjects have the same unplanned infusion parameter level, a column labelled with this unplanned level will be added. This unplanned column will not be included in the table shell but will only be inserted into the table output as necessary.

Protocol deviations may result in an invalid infusion even if there is adherence to the criteria as stated in [Table 2](#). The following protocol deviations will lead to invalidation of an infusion (this will have no impact on the assignment of a subject to the analysis sets):

- Prohibited concomitant medication
  - Any medications with the primary purpose of masking local or systemic AEs (including but not limited to analgesics and anesthetics  $\pm$  12h around the infusion).
  - Any Ig product other than the study medication

These protocol deviations will be assessed on an infusion basis, not on a subject basis. Prior to DB lock, the infusion data will be merged with the concomitant medication data so that the start date of an infusion can be compared with the start date of concomitant medication. This list will be provided to CSL as an Excel file. CSL will manually review this file and flag the infusions which will have to be considered invalid due to prohibited concomitant medication. Only concomitant medication with complete start dates can be considered in the merge to infusion data.

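### Masking medication invalidates an infusion, but for home infusions its recording is scheduled only at 4-weekly visits, so responder rates may be overstated by an unknown amount

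*Protocol*

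**What the plan says.** **The rule.** Protocol 7.3 prohibits drugs whose main purpose is to mask adverse events, and names "analgesics and anesthetics +/-12h around the infusion". Protocol 14.4 warns that such use can invalidate an infusion that otherwise met its parameters. SAP 11.1 makes this definite: "The following protocol deviations will lead to invalidation of an infusion", and prohibited concomitant medication is what it then lists. Valid infusions define responders: at least 3 of 4 in the pump cohorts, and the minimum k of Protocol Table 7 in manual push. A level succeeds at 33% responders or more, and the highest successful level becomes the label recommendation (Protocol 11.3.5, SAP 11.1).

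**The recording.** Both schedules of assessments mark concomitant therapies at Screening, Day 1, the 4-weekly office visits and End of Study. The home-week lists in Protocol 8.4.2 and 8.4.3 hold two items. For the Pump-Assisted Flow Rate Cohort they read "Administer IgPro20. Infusion data should be recorded in the subject eDiary / back-up paper diary" and "Evaluate for AEs (including injection site reaction[s]) and record any findings in the subject eDiary / back-up paper diary"; the lists for the other cohorts match in content. None mentions medication. Footnote c of both schedules states that the "eDiary will be used for collecting infusion parameters and adverse events", and Protocol 14.5.1 describes home entries in the same way.

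**The definition.** Protocol 8.3 treats as concomitant therapy "All drugs and/or procedures currently being administered to a subject at the time of signing informed consent, and which continue to be taken" alongside IgPro20.

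**The match.** Before database lock, SAP 11.1 merges medication with infusion data so that start dates can be compared. The sponsor then flags invalid infusions by manual review. Medication without a complete start date does not enter the merge.

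**The concern.** A 24-hour window around each infusion decides part of the primary endpoint. For most infusions, the protocol schedules no question about that window until the next office visit. Adverse events, by contrast, are recorded at home in every infusion week.

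The error from forgotten use goes one way: a drug that is not recalled leaves the infusion valid. A drug that is recalled with only a partial date has the same result, because it drops out of the merge, and recall over weeks makes partial dates more likely. No imputation is planned for missing data (Protocol 11.3.5), and no sensitivity analysis covers this point.

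Read literally, section 8.3 also leaves out a painkiller or numbing product first used after consent, which is the use that the rule is meant to catch.

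**Working it through.** **1. Share of infusions that rest on recall.** Protocol 6.3 and the visit lists give one office visit, with an observed infusion, every 4 weeks. This is taken as one supervised infusion per level.

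- Pump cohorts: (4 − 1)/4 = 75%.
- Manual push, 2 per week: (8 − 1)/8 = 87.5%.
- Manual push, 7 per week: (28 − 1)/28 = 96.4%.

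Recall time on scheduled days: pump home infusions on Days 8, 15 and 22 are first asked about on Day 29, after 21, 14 and 7 days. A daily manual push subject's Day 2 infusion is asked about after 27 days. The 12 hours after the Day 1 infusion are asked about after 28 days.

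**2. The plan's own figures.** With 15 subjects and a true responder rate of 50%:

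P(X ≥ 5) = 1 − (1 + 15 + 105 + 455 + 1365)/32768 = 1 − 1941/32768 = 0.9408, against the stated 94%. It reproduces, and it does not depend on how medication is recorded.

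For a single infusion at 61%: 4 × 0.61³ × 0.39 + 0.61⁴ = 0.4925. Exactly 50% needs 0.6143, so 61% is a rounded value.

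**3. How a missed drug reaches the endpoint.** A pump subject with two unrecalled masked home infusions counts as 4 of 4 (responder) instead of 2 of 4 (non-responder). At the threshold, one such subject moves a cohort from 4/15 = 26.7% (fails) to 5/15 = 33.3% (meets the criterion).

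**4. Size under an assumed range.** The documents give no rate of unrecorded use. Let m be the share of apparently valid pump home infusions that in truth had a prohibited drug, q the apparent validity, and h = q(1 − m) the true validity at home. With one supervised and three home infusions:

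true responder rate = h³ + q × 3h²(1 − h)

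With q = 0.6143, the apparent rate is 50.0% and P(at least 5 of 15) is 0.941. For m = 20%, h = 0.4914, so the rate is 0.1187 + 0.6143 × 0.3685 = 34.5%.

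| Assumed m | True responder rate | Overstatement (points) | P(at least 5 of 15) at true rate |
|---|---|---|---|
| 5% | 46.0% | 4.0 | 0.895 |
| 10% | 42.1% | 7.9 | 0.828 |
| 20% | 34.5% | 15.5 | 0.633 |
| 30% | 27.4% | 22.6 | 0.394 |

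If apparent validity is 0.90, m = 20% lowers the responder rate from 94.8% to 76.5%, but P(success) stays at about 1.00.

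**5. The recording texts side by side.** Section 8.3 covers drugs in use at consent and continued. Section 8.4.1 starts the recording of concomitant therapies at Screening, and each office visit and End of Study asks for use of any concomitant therapy. SAP 9.4 has a class, 'Concomitant Only', for drugs started on or after first treatment, and its listing carries start and end date and time. These passages cannot all be read literally.

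**The case against.** The strongest reply is that capture is delayed, not absent. Office visits ask about any therapy, and SAP 9.4 expects drugs started during the study, with dates, times and a linked adverse event where there is one. A reader of 8.3 alone might infer that newly started analgesics go unrecorded. The visit lists and SAP 9.4 contradict that; 8.3 is a wording conflict.

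A reader might also infer that the diary holds no medication item. Footnote c says what the eDiary is for, not that it holds nothing else. Protocol 14.5.2 mentions diary training on drug usage, which may or may not mean IgPro20 only. SAP section 3 cites an eDiary screen report and annotated eCRFs that are not among the documents, so such an item cannot be ruled out. The protocol does not require one, however.

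Nor do the documents show that the rates are in fact biased upward. Under-recording can only raise them, but its frequency is not given. Date-only matching can err the other way, by flagging a same-day drug taken outside the 12 hours, subject to the manual review. The threshold example is also a narrow case: at the planning rate, exactly 5 of 15 has probability 3003/32768 = 9.2%.

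Two further inferences fail. The over-the-counter allowance in 7.2 does not weaken the rule, since its first item excludes masking drugs and 7.3 names them. The order of bullets at level-change visits is not a sequence (diary review precedes the infusion at Week 5 and follows it at Week 9 in the Flow Rate Cohort), and the medication flag is settled before lock.

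What stands is the mismatch between a 24-hour window and recall over weeks.

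**Conclusion.** The point holds as a weakness in data capture for a component of the primary endpoint. For 75% of pump infusions and 87.5% to 96.4% of manual push infusions per level, the prohibited-medication criterion rests on later recall, on the assumption of one supervised infusion per level. Responder rates may be overstated by an unknown amount. At the planning value, the assumed range of 5% to 30% corresponds to about 4 to 23 percentage points in the pump cohorts. If true validity is high, the success decision hardly changes.

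The stated 94% is correct and unaffected. Section 8.3 conflicts with the visit lists and with SAP 9.4, and must be reconciled with them. Confidence is moderate, because the eDiary screens and the eCRF could not be checked. The change should be made, since it is cheap and replaces recall by measurement.

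**What to change.** 1. Reword Protocol 8.3 to cover every therapy used from consent to End of Study, including those started after consent.
2. Add one question per infusion to the eDiary and the back-up paper diary, unless the eDiary already has it: any pain-relieving or numbing medicine in the 12 hours before or after this infusion, with name, date and time. The part about the hours afterwards is answered at the next entry.
3. Add this item to the home-week lists in 8.4.2 and 8.4.3 and to both schedules.
4. In SAP 11.1, base the invalidation flag on this item, by date and time.
5. If data have already been collected without it, add a sensitivity analysis that counts infusions with unknown or partially dated medication as invalid.

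The cost is one diary question, one line on paper and some wording. It takes the subject a few seconds per infusion, and responder rates may come out slightly lower.

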8.4 Visit Schedule

The timing and frequency of the study visits are described in the [Schedule of Assessments](#). Time windows for all assessments are detailed in Table 5.

Table 5. Time Windows for Assessments

Visit / Procedure	Time window (relative to scheduled visit / procedure)
Screening	Between Day -35 and -7.
Vital signs	± 5 min
Blood collection for clinical laboratory tests	Between Day -35 and -7 and at the End of Study visit on Day 85 (±1) day (Day 113 [±1] day for the Pump-Assisted Flow Rate Cohort).
Blood collection for IgG	On Day 1 and End of Study visit (within approximately 1 hour before next infusion).

8.4.1 Screening

All subjects, or the subjects' parent(s) or legally acceptable representative(s), must provide written informed consent before any study-specific assessments or procedures are performed. Written informed consent is not required for assessments or procedures performed according to standard of care (eg, for diagnosis or treatment); results from such assessments may be used in the determination of study eligibility.

A Screening examination should be performed between Day -35 and -7. The following procedures will be conducted and documented at the Screening visit:

- Obtain written informed consent.
- Review inclusion/exclusion criteria.
- Record information regarding medical history and demographics.
- Collect blood sample for beta-human chorionic gonadotropin for females of child-bearing potential.
- Perform a physical examination.
- Measure vital signs:
 - Systolic blood pressure, diastolic blood pressure, respiratory rate, pulse rate, and body temperature
 - Body weight
 - Height
- Collect blood samples for laboratory safety evaluation (biochemistry and hematology).
- Start recording AEs and use of concomitant therapies.

Subjects who complete all of these assessments and who fulfil the eligibility criteria (ie, eligible subjects) will be enrolled into the study. If the subject is not eligible for the study, the primary reason for screen failure must be entered in the eCRF.

8.4.2 Pump-Assisted Flow Rate Cohort

8.4.2.1 Week 1 (Day 1)

The following procedures will be conducted and documented at this **office visit**:

- Review inclusion/exclusion criteria.
- Measure systolic blood pressure, diastolic blood pressure, respiratory rate, pulse rate, and body temperature.
- Collect blood sample for IgG trough level assessment (within approximately 1 hour before infusion).
- Train subjects on how to use pump for infusion of IgPro20.
- Train subjects on how to use the subject eDiary / back-up paper diary.
- Supervised infusion of IgPro20. Supervised entry of infusion data in the subject eDiary / back-up paper diary.
- IgPro20 dispensation and IRT update.

- Evaluate for AEs (including injection site reaction[s]), record any findings in the eCRF. Train subjects to record AEs in the subject eDiary / back-up paper diary. Confirm that AEs have been recorded in the subject eDiary / back-up paper diary.
- Record use of any concomitant therapy(ies).

8.4.2.2 Weeks 2 (Day 8±1), 3 (Day 15±1) & 4 (Day 22±1)

The following procedures will be conducted and documented **at home**:

- Administer IgPro20. Infusion data should be recorded in the subject eDiary / back-up paper diary.
- Evaluate for AEs (including injection site reaction[s]) and record any findings in the subject eDiary / back-up paper diary.

